Study Objectives	
Primary objective is to determine whether an initial invasive (INV) strategy of cardiac catheterization and optimal revascularization, if feasible, in addition to optimal medical therapy (OMT) in patients with stable ischemic heart disease (SIHD) and at least moderate ischemia on ischemia testing reduces the incidence of the composite of death or nonfatal myocardial infarction compared with a conservative (CON) strategy of optimal medical therapy alone with cardiac catheterization and revascularization reserved for failure of OMT, in participants with advanced CKD (defined as those with estimated glomerular filtration rate [eGFR] <30 or on dialysis).
 
Secondary objective is to determine whether an INV strategy is more effective than CON strategy in improving angina control, as assessed by the Seattle Angina Questionnaire (SAQ) Angina Frequency scale, and disease-specific quality of life, as assessed by the SAQ Quality of Life scale.
 
Other secondary objectives include comparing the incidence of the composite of cardiovascular death, nonfatal myocardial infarction, resuscitated cardiac arrest, or hospitalization for unstable angina or heart failure; individual components of this endpoint; all-cause death; stroke; as well as comparing health resource utilization, cost, and cost-effectiveness between the two randomized strategies.

Study Design	ISCHEMIA-CKD is an international comparative effectiveness study. Participants will be recruited following clinically indicated ischemia testing and randomized in a 1:1 fashion to an INV or CON strategy.
Number of Participants	Approximately 1,000 participants randomized
Trial Location	Multinational: approximately 500 sites worldwide
Inclusion Criteria	
 • At least moderate ischemia on an ischemia test (see definitions in protocol appendix A) • End stage renal disease on dialysis or estimated glomerular filtration rate (eGFR) <30mL/min • Participant is willing to comply with all aspects of the protocol, including adherence to the assigned strategy, medical therapy and follow-up visits

	
 • Participant is willing to give written informed consent • Age ≥ 21 years
Exclusion Criteria	
 • LVEF < 35% • History of unprotected left main stenosis ≥50% on prior coronary computed tomography angiography (CCTA) or prior cardiac catheterization (if available) • Finding of “no obstructive CAD” (<50% stenosis in all major epicardial vessels) on prior CCTA or prior catheterization, performed within 12 months • Coronary anatomy unsuitable for either PCI or CABG • Unacceptable level of angina despite maximal medical therapy • Very dissatisfied with medical management of angina • History of noncompliance with medical therapy • Acute coronary syndrome within the previous 2 months • PCI within the previous 12 months • Stroke within the previous 6 months or spontaneous intracranial hemorrhage at any time • History of ventricular tachycardia requiring therapy for termination, or symptomatic sustained ventricular tachycardia not due to a transient reversible cause • NYHA class III-IV heart failure at entry or hospitalization for exacerbation of chronic heart failure within the previous 6 months • Non-ischemic dilated or hypertrophic cardiomyopathy • Severe valvular disease or valvular disease likely to require surgery or percutaneous valve replacement during the trial • Allergy to radiographic contrast that cannot be adequately pre-medicated, or any prior anaphylaxis to radiographic contrast • Planned major surgery necessitating interruption of dual antiplatelet therapy (note that patients may be eligible after planned surgery) • Life expectancy less than the duration of the trial due to non-cardiovascular comorbidity • Pregnancy (known to be pregnant; to be confirmed before randomization, if applicable) • Patient who, in the judgment of the patient’s physician, is likely to have

	
significant unprotected left main stenosis
 
 • Enrolled in a competing trial that involves a non-approved cardiac drug or device • Inability to comply with the protocol • Exceeds the weight or size limit for cardiac catheterization at the site • Canadian Cardiovascular Society Class III angina of recent onset, OR angina of any class with a rapidly progressive or accelerating pattern • Canadian Cardiovascular Society Class IV angina, including unprovoked rest angina • High risk of bleeding which would contraindicate the use of dual antiplatelet therapy • Cardiac transplant recipient • Prior CABG, unless CABG was performed more than 12 months ago, and coronary anatomy has been demonstrated to be suitable for PCI or repeat CABG to accomplish complete revascularization of ischemic areas (CCC approval required)
Primary Endpoint	Time to first occurrence of death or nonfatal myocardial infarction.
Secondary Endpoints	
 • Angina control per SAQ Angina Frequency Scale • Disease-specific quality of life per SAQ Quality of Life Scale • Composite of cardiovascular death, nonfatal myocardial infarction, or stroke • Composite of cardiovascular death, nonfatal myocardial infarction, resuscitated cardiac arrest, or hospitalization for unstable angina or heart failure • All-cause death • Cardiovascular death • Nonfatal MI • Resuscitated cardiac arrest • Hospitalization for unstable angina • Hospitalization for heart failure • Stroke • Composite of cardiovascular death, nonfatal myocardial infarction, stroke, resuscitated cardiac arrest, hospitalization for unstable angina

	
or heart failure.
 
 • Health resource utilization, costs, and cost-effectiveness
Assessment Schedule	Pre-eligibility screening, randomization, 1.5 months, 3 months, 6 months, 12 months, and every 6 months thereafter.
Study Duration	Enrollment will occur over approximately 3.5 years with an expected minimum of 18-24 months follow-up and an average of approximately 4 years follow-up.
Clinical Event Adjudication Committee	The following events will be adjudicated by a blinded Clinical Event Adjudication Committee: death, myocardial infarction, resuscitated cardiac arrest, hospitalization for unstable angina, hospitalization for heart failure, and stroke.
Data and Safety Monitoring Board	An independent Data and Safety Monitoring Board will advise the NHLBI and study leadership on safety aspects and overall progress of the study.
Statistical Considerations	A sample size of approximately 1,000 randomized participants is expected to provide ≥80-95% power to detect a 15%-19% reduction in the primary composite event rate in participants randomized to INV as compared with CON strategy.

TABLE OF CONTENTS

1.	LIST OF ABBREVIATIONS AND DEFINITIONS.....	11
2.	BACKGROUND AND RATIONALE.....	15
3.	STUDY OBJECTIVES	16
4.	STUDY DESIGN.....	17
4.1	Study Flow	17
4.2	Study Population.....	19
4.3	Inclusion/Exclusion Criteria	19
4.3.1	Criteria Prior to Informed Consent	19
4.3.2	Criteria After Enrollment (Informed Consent) and Prior to Randomization	20
5.	STUDY PROCEDURES	21
5.1	Qualifying Ischemia Test.....	21
5.2	Informed Consent Process	21
5.3	Interactive Voice Response System (IVRS) and Interactive Web Response System (IXRS).....	21
5.4	Core Lab Ischemia Verification.....	22
6.	MANAGEMENT STRATEGIES	23
6.1	Conservative (CON) Strategy.....	23
6.2	Invasive (INV) Strategy	23
6.3	Optimal Medical Therapy (OMT).....	23
6.3.1	Management of Angina in CON Participants.....	24
6.3.2	Management of Angina in INV Participants	24
6.4	Optimal Revascularization Therapy (ORT)	24
6.4.1	Criteria to Select PCI vs. CABG	25
6.4.2	Guidelines for Optimal Percutaneous Coronary Intervention.....	25
6.4.3	Guidelines for Optimal Surgical Revascularization	25
6.5	Maximizing Adherence to CON Strategy.....	25
6.6	Cath in Participants Randomized to CON Strategy	26
7.	AUXILLIARY SCREENING LOG	28
7.1	Screening Log.....	28
8.	Study Assessments	29
8.1	Creatinine and Pregnancy Test.....	29
8.2	Standard Blood Tests.....	29
8.3	Endpoint Assessments.....	29

8.4	Blood Biomarkers and Genomics Biorepository	29
8.5	Medication Adherence	30
8.6	Lifestyle Assessment	30
8.7	Quality of Life Assessment.....	30
8.8	Economics Assessment.....	30
9.	SCHEDULE OF ASSESSMENTS	31
10.	ADJUDICATION OF CLINICAL EVENTS	40
11.	STATISTICAL CONSIDERATIONS AND ANALYSIS PLAN	41
11.1	Sample Size Determination and Statistical Power	41
11.1.1	Summary of Power and Precision	41
11.2	Statistical Analysis Plan	41
11.2.1	Analysis of the Primary Endpoint	42
11.2.2	Analysis of the Secondary Endpoints	42
11.2.3	Contingency Plan For Insufficient Primary Endpoint Events	43
11.2.4	Quality of Life (QOL) Analysis.....	43
11.2.5	Health Economics Analysis	44
11.2.6	Interim Analysis	44

1. LIST OF ABBREVIATIONS AND DEFINITIONS

ACC	American College of Cardiology
ACE-I	angiotensin converting enzyme inhibitor
ACS	acute coronary syndrome
AHA	American Heart Association
AST	aspartate aminotransferase
ALT	alanine aminotransferase
BARI 2D	Bypass Angioplasty Revascularization Investigation 2 Diabetes trial
CABG	coronary artery bypass graft
CAD	coronary artery disease
Cath	cardiac catheterization
CCC	Clinical Coordinating Center
CCS	Canadian Cardiovascular Society
CEC	clinical event adjudication committee
CI	confidence interval
CKD	Chronic kidney disease (defined as those with estimated glomerular filtration rate [eGFR] <30 or on dialysis)
CK-MB	creatinine kinase-MB
CL	Core laboratory
CMR	cardiac magnetic resonance
CON	Conservative management strategy (initial management with OMT alone, with cath and revascularization reserved for refractory symptoms or acute ischemic events)
COURAGE	Clinical Outcomes Utilizing Revascularization and Aggressive Drug Evaluation trial
CV	Cardiovascular
DASI	Duke Activity Status Index

DNA	deoxyribonucleic acid
DSMB	Data and Safety Monitoring Board
ECG	Electrocardiogram
Echo	echocardiography
eCRF	electronic case report form
EDC	electronic data capture
EDTA	ethylenediaminetetraacetic acid
ERES	electronic signature
eGFR	estimated glomerular filtration rate
EQ-5D	self-reported generic preference-based measure of health, developed by the EuroQol Group
EQOL	economic and quality of life
EQOLCC	EQOL Coordinating Center
ESC	European Society of Cardiology
ETT	Exercise tolerance testing
EU Directive	European Union Directive on Data Privacy
FFR	fractional flow reserve
HbA1c	hemoglobin A1c
HDL	high density lipoprotein
HF	heart failure
HIPAA	Health Insurance Portability and Accountability Act
HR	Hazard Ratio
ICC	Ischemia Imaging Coordinating Center
ICH	International Conference on Harmonization
IEC	institutional ethics committee
INV	invasive management strategy (cath with intent to perform optimal

	revascularization plus optimal medical therapy)
IRB	Institutional Review Board
ISCHEMIA	International Study of Comparative Health Effectiveness with Medical and Invasive Approaches trial
IVRS	interactive voice response system
IVUS	intravascular ultrasound
IXRS	interactive web response system
LM CAD	left main coronary artery disease
LOT-R	Life Orientation Test – Revised
LVEF	left ventricular ejection fraction
MI	myocardial infarction
MOE	margin of error
MOO	Manual of Operations
MPI	myocardial perfusion imaging
NHLBI	National Heart, Lung, and Blood Institute
NIH	National Institutes of Health
NINDS	National Institute of Neurological Disorders and Stroke
NYHA	New York Heart Association
OMT	optimal medical therapy
ORT	optimal revascularization therapy
PACE	Patient-centered Assessment and Counseling for Exercise and nutrition
PCI	percutaneous coronary intervention
PET	positron emission tomography
PHI	protected health information
PHQ-8	Patient Health Questionnaire-8
PI	Principal Investigator

PIPEDA	Personal Information Protection and Electronic Documents Act
PSS	Perceived Stress Scale
REB	Research Ethics Board
RNA	ribonucleic acid
SAC	statistical analysis center
SAQ	Seattle Angina Questionnaire
SDCC	Statistical and Data Coordinating Center
SIHD	stable ischemic heart disease
SPECT	single photon emission computed tomography
WHF	World Heart Federation

2. BACKGROUND AND RATIONALE

Among patients with advanced CKD, cardiovascular disease is the leading cause of death,^{1,2} 15-30 times higher than the age-adjusted cardiovascular mortality rate in the general population.^{3,4} The projected 4-year mortality is >50% in patients with advanced CKD⁵⁻⁹ and is worse than that for patients in the general population who have cancers, heart failure, stroke or MI.¹⁰ Participants with advanced CKD are 5-10 times more likely to die than to reach end stage renal disease (ESRD).¹¹ Despite this, ~80% of contemporary coronary artery disease (CAD) trials exclude participants with advanced CKD.¹² Most of the treatments aimed at reducing cardiovascular events in advanced CKD are therefore extrapolated from cohorts without advanced CKD. Participants with advanced CKD and cardiovascular disease are undertreated with less frequent use of statins and revascularization therapies, and the optimal management approach to these patients is unknown. Participants with advanced CKD are notably underrepresented in contemporary trials comparing revascularization with medical therapy in SIHD patients, such as the Bypass Angioplasty Revascularization Investigation 2 Diabetes (BARI 2D) trial¹³ or the Clinical Outcomes Utilizing Revascularization and Aggressive Drug Evaluation (COURAGE) trial,¹⁴ making any assessment about the efficacy of revascularization plus medical therapy vs. initial medical therapy alone in this cohort problematic.

Participants with advanced CKD are at increased risk for complications of the assigned invasive procedure, specifically contrast-induced acute kidney injury (AKI),^{15,16} dialysis, major bleeding and short-term risk of death. However, there is controversy in the medical literature regarding the incidence (<1% to >30%), effective treatment (saline hydration, N-acetyl cysteine, or sodium bicarbonate) and prognosis of contrast induced AKI (<0.5% to >5% requiring dialysis).¹⁷⁻²⁰ In addition although contrast induced AKI have been associated with increase in short-term mortality residual confounding in these studies makes interpretation difficult. Moreover it is unknown if these short-term increased risks are offset by long-term benefits. Limited observational study in the CKD cohort suggests a survival benefit of revascularization when compared with medical therapy alone long-term,²¹⁻²⁴ despite increase in short-term risks. However, the medical therapy in these trials was not optimized, drug eluting stents were rarely used and there is undoubtedly inherent selection and ascertainment bias with observational studies. The above has resulted in **substantial clinical equipoise in the management of these patients with the rates of revascularization of only around 10-45%.**^{21,23,25} The results of ISCHEMIA-CKD will have profound implications for guidelines, health policy, and clinical practice.

3. STUDY OBJECTIVES

PRIMARY AIM

The primary aim of the ISCHEMIA-CKD trial is to determine whether an initial invasive strategy of cardiac catheterization and optimal revascularization, if feasible, in addition to OMT, will reduce the primary composite endpoint of death or nonfatal myocardial infarction in participants with SIHD and at least moderate ischemia over an average follow-up of approximately 4 years compared with an initial conservative strategy of OMT alone with catheterization reserved for failure of OMT, in participants with advanced CKD.

SECONDARY AIMS

The secondary aims are to compare the following clinical and economic outcomes in participants randomized to INV or CON strategies:

- Angina control, as assessed by the Seattle Angina Questionnaire (SAQ) Angina Frequency scale
- Disease-specific quality of life, as assessed by the SAQ Quality of Life
- Composite of cardiovascular death, nonfatal myocardial infarction, or stroke
- Composite of cardiovascular death, nonfatal myocardial infarction, resuscitated cardiac arrest, or hospitalization for unstable angina or heart failure
- All-cause death
- Cardiovascular death
- Nonfatal MI
- Resuscitated cardiac arrest
- Hospitalization for unstable angina
- Hospitalization for heart failure
- Stroke
- Composite of cardiovascular death, nonfatal myocardial infarction, stroke, resuscitated cardiac arrest, or hospitalization for unstable angina or heart failure.
- Health resource utilization, costs, and cost-effectiveness

4. STUDY DESIGN

The ISCHEMIA-CKD trial is an international, randomized, comparative effectiveness study. Approximately 1,000 participants at approximately 500 sites worldwide with advanced CKD (defined as eGFR<30 or on dialysis) and at least moderate ischemia on ischemia testing will be randomized in a 1:1 fashion to the INV or CON strategies.

The design of the trial to randomize patients upstream of cath is advantageous as it will expose only 50% of participants (enrolled to INV) to contrast agent and will be the largest treatment strategy trial in advanced CKD patients with SIHD.

[figure not shown]
ISCHEMIA-CKD is designed to run in parallel with its parent study, ISCHEMIA, which randomizes patients with eGFR >30, SIHD, and at least moderate ischemia in 1:1 fashion to the INV or CON strategies.

4.1 Study Flow

See figure 1 for details. Patients with advanced CKD and at least moderate ischemia (see section 5.1) will be identified and screened for clinical inclusion/exclusion criteria (see section 4.3). Patients who are suspected to be trial eligible may also be pre-screened, for example, prior to clinically indicated ischemia testing in clinical areas where SIHD patients are cared for. Patients who meet clinical and ischemia (site-interpreted) eligibility criteria and are interested in participating in the trial will be enrolled by signing an informed consent and receiving a study number via the interactive voice response system (IVRS) or interactive web response system (IXRS) (see section 5.3). Ischemia test data (e.g., images, ECG, report) will be transferred to the relevant core lab electronically for enrolled participants (see Figure 1).

Participants with known or a high likelihood of unprotected left main stenosis $\geq 50\%$ will be excluded before randomization. Timing of Randomization: Participants determined to be eligible for randomization should be randomized within a target of 15 days of consent, and participants randomized to INV strategy should undergo catheterization within a target of 30 days after randomization, with optimal revascularization therapy (ORT) soon thereafter as appropriate. Participants will be enrolled over approximately 3.5 years. Randomized participants will be followed for an average of approximately 4 years. The minimum follow-up period for randomized participants will be approximately 18-24 months following randomization of the final participant. A schedule of assessments is provided in [section 9](#).

Figure 1 Study Flow

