9. SCHEDULE OF ASSESSMENTS

Overview of Visits

All participants will undergo eligibility screening, informed consent and randomization procedures.

Follow-up in randomized participants will occur at 1.5, 3, 6, and 12 months following randomization during the first year and every 6 months thereafter, with clinic visits, phone follow-up, and other testing as described below (See [Table 2](#) for complete assessment schedule). The schedule of assessments ([Table 2](#)) specifies the preferred method of contact for each visit. Six-month visits may be via telephone or email, depending on participant stability, risk factor control, and the participant's distance from the clinic ("geography") ([see Table 2](#)). In the event that a scheduled clinic visit is not possible, to ensure participant follow-up other forms of contact should be used, such as telephone, email, communication from a personal physician, other allied health professional, or family member, or review of electronic health record or public records. After the first year, participants will be followed every 6 months until the end of the trial, at which time sites will be notified to perform a closeout visit.

Dependent on additional funding, telephone or email follow-up every 6 months or ascertainment of database information on vital status may continue after all clinic visits have been completed, unless prohibited by local regulations. At these long-term follow-up contacts, information on current health and medications, and interval hospitalizations will be collected.

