11. STATISTICAL CONSIDERATIONS AND ANALYSIS PLAN

11.1 Sample Size Determination and Statistical Power

11.1.1 Summary of Power and Precision

As shown in Tables 3 and 4 below, the planned sample size of approximately 1,000 randomized participants will result in an estimate of the hazard ratio that differs from the true hazard ratio by no more than a factor of 1.19 with 95% probability and will yield power $\geq 80-95\%$ for comparing the primary composite endpoint across the two randomized groups assuming the 4-year cumulative rate of the primary composite endpoint is 60% in participants randomized to CON strategy and is less by a factor of 15% to 19% (relative reduction) in participants randomized to INV strategy. Power and precision under other assumptions are summarized in [Table 5](#) and [Table 6](#) below.

CON anticipated 4-year event rate	Power		
	$\Delta = 0.15$	$\Delta = 0.17$	$\Delta = 0.19$
Event %			
45%	56	67	76
50%	64	75	84
55%	73	83	90
60%	81	90	95
65%	88	95	98
70%	94	98	99

NOTE: Δ denotes relative reduction in 4-year event rate in INV vs. CON groups. **Assumptions:** Two-sided log-rank test with $\alpha = 0.05$; 500 participants per group; average follow-up 3.7 years; loss-to-follow-up 1% per year; survival times follow exponential distribution.

CON anticipated 4-year event rate	Margin of Error (MOE)		
	$\Delta = 0.15$	$\Delta = 0.17$	$\Delta = 0.19$
Event %			
45%	1.22	1.22	1.23
50%	1.21	1.21	1.21
55%	1.20	1.20	1.20
60%	1.19	1.19	1.19
65%	1.18	1.18	1.18
70%	1.17	1.18	1.18

NOTE: Margin of Error is the anti-log of the expected half-width of the 95% confidence interval for the log-hazard ratio. Assumptions: Based on a univariable Cox model with a binary treatment indicator and Wald-type 95% confidence intervals.

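### Does the gap between a 3.7-year and an approximately 4-year average follow-up undermine the stated power?

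*Combined protocol and SAP*

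**What the plan says.** The Study Duration entry of the synopsis reads: "Enrollment will occur over approximately 3.5 years with an expected minimum of 18-24 months follow-up and an average of approximately 4 years follow-up". The primary aim in section 3 is framed "over an average follow-up of approximately 4 years". Section 4.1 repeats the enrolment period and the average, "Participants will be enrolled over approximately 3.5 years. Randomized participants will be followed for an average of approximately 4 years", and adds: "The minimum follow-up period for randomized participants will be approximately 18-24 months following randomization of the final participant".

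The note to the power table in section 11.1.1 uses a shorter value, "average follow-up 3.7 years", with 500 participants per group, 1% loss per year, exponential survival and a two-sided log-rank test at 0.05. From this the synopsis concludes that the sample size "is expected to provide ≥80-95% power to detect a 15%-19% reduction in the primary composite event rate". Section 11.1.1 adds that the estimated hazard ratio "differs from the true hazard ratio by no more than a factor of 1.19 with 95% probability".

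On ending the trial, section 9 says participants are seen every six months "until the end of the trial, at which time sites will be notified to perform a closeout visit". Section 11.2.3 provides for a review of aggregate event data that projects the final event count. If power falls below 90%, extending follow-up is the first of the options to be considered.

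**The concern.** Two things look wrong on a first reading. The average follow-up is 3.7 years where power is calculated and about 4 years elsewhere. And enrolment over 3.5 years with a minimum of 18 to 24 months does not by itself secure either value, because the average also depends on how quickly participants enter, which is not stated.

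In an event-driven comparison, follow-up determines the number of events and hence power. If the trial closed at the short end of its range after even or slow enrolment, power for a 15% reduction would fall below the stated 80% floor and the margin of error would exceed 1.19. Neither statement carries a condition on accrual or close-out, so a reader could take them as assured by the schedule.

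**Working it through.** **Inputs.** From the tables and notes in 11.1.1: 500 per arm, two-sided alpha 0.05, loss 1% per year, exponential survival, a 60% four-year rate in the conservative (CON) arm, relative reductions of 15, 17 and 19%, average follow-up 3.7 years. From 4.1: enrolment 3.5 years (42 months), minimum 18-24 months. The accrual shapes below are my assumptions. Follow-up is counted from randomization to close-out.

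**Formulas.**
- Hazard: λ = −ln(1 − p)/4. CON: −ln(0.40)/4 = 0.2291. Invasive (INV) arm at a 15% reduction: p = 0.51, −ln(0.49)/4 = 0.1783, so HR = 0.779. For 17% and 19% the HRs are 0.752 and 0.726.
- Loss hazard: g = −ln(0.99) = 0.01005.
- Expected events per arm: 500 × mean over follow-up times t of [λ/(λ+g)] × [1 − exp(−(λ+g)t)].
- Power (Schoenfeld): Φ(½√D × |ln HR| − 1.96), where D is total events.
- Margin: exp(1.96 × √(1/e₁ + 1/e₂)), where e₁ and e₂ are events per arm.

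**Step 1: reproduce the plan's figures.** With t fixed at 3.7 years and a 15% reduction, expected events are 281.3 (CON) and 237.6 (INV), D = 519. Power = Φ(½√519 × 0.2504 − 1.96) = 81.4%. Margin = exp(1.96 × √(1/281.3 + 1/237.6)) = 1.19. Across the three reductions power is 81.4/89.7/95.0%, against the printed 81/90/95. All 18 power cells agree within 0.6 points and all 18 margin cells within 0.006. With even staggered entry averaging 3.7 years, the 60% row is 80.6/89.2/94.6%.

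**Step 2: what the schedule implies.** For any accrual pattern, average follow-up = 42 − mean entry month + minimum, in months.
- An average of 3.7 years (44.4 months) needs a mean entry month of 42 + 18 − 44.4 = 15.6, or 42 + 24 − 44.4 = 21.6.
- An average of exactly 4.0 years (48 months) needs month 12.0 or 18.0.
- Even enrolment has mean entry at month 21, so the average is 39 months (3.25 years) with an 18-month minimum and 45 months (3.75 years) with 24.

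**Step 3: power at the 60% CON rate.**

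| Enrolment (assumed) | Minimum, months | Average, years | Power, 15/17/19% | Margin |
|---|---|---|---|---|
| Even | 18 | 3.25 | 77.0/86.3/92.6 | 1.20 |
| Even | 24 | 3.75 | 81.0/89.4/94.8 | 1.19 |
| Linearly front-loaded | 18 | 3.83 | 82/90/95 | 1.19 |
| Linear slow start | 18 | 2.67 | 71.2/81.3/88.8 | 1.22 |
| Linear slow start | 24 | 3.17 | 76.5/85.9/92.3 | 1.20 |

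At a 15% reduction, 80% power needs 4 × (1.960 + 0.8416)²/(ln 0.7785)² = 501 events. Even enrolment reaches that with a minimum of about 22.4 months, inside the stated range.

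**Step 4: the effect of 3.7 against 4.** Even enrolment averaging 4.0 years gives 82.6/90.7/95.6%. Compared with even entry averaging 3.7 years, that is higher by 82.6 − 80.6 = 2.0, 90.7 − 89.2 = 1.5 and 95.6 − 94.6 = 1.0 points. The power section uses the less favourable value.

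**The case for a change.** The strongest case for acting is that Step 2 needs no accrual assumption. At the 18-month end, 3.7 years requires entry clearly weighted to the early months, and a literal 4.0 years requires early weighting at both ends. The plan states no such condition. A slow start is a plausible pattern, and under it 80% power at a 15% reduction is reached nowhere in the 18-24 month range; it needs about 28.9 months. The extension in 11.2.3 is something to be considered, not automatic, and section 9 ties close-out neither to an event count nor to an average.

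The arithmetic stands, and so does the observation that the accrual pattern is unstated. It does not carry the conclusion, for three reasons.

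- The minimum is not the only statement about duration. The average of about 4 years is stated separately, and every scenario above that falls below 80% has an average of 3.25 years or less, which does not fit that statement.
- The projection in 11.2.3 would register short follow-up as well as a low event rate. If its 90% target refers to the 17% reduction, where the table prints 90, then even enrolment with an 18-month minimum (86%) would trigger the review. Section 11.2.6 also has the monitoring board review recruitment and control-group event rates.
- The obvious remedy, closing out at a fixed number of events, has a real cost. About 510 events reproduce the printed 60% row under any accrual pattern, but with a slow start they arrive 30.1-31.6 months after the last randomization. At a 55% CON rate with even enrolment they arrive at 29.6-31.3 months, and power at a 15% reduction is then still only 76%.

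**Conclusion.** No change is needed. No printed figure is wrong: the tables are correct for the follow-up they disclose, and even enrolment with a minimum near 24 months delivers them within the plan's own range. The difference between 3.7 and approximately 4 years is one of rounding, and it errs on the cautious side by about 1 to 2 points of power.

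The exposure under even enrolment is confined to the short end of the range. With an 18-month minimum, power is lower than printed by 81 − 77.0 = 4.0, 90 − 86.3 = 3.7 and 95 − 92.6 = 2.4 points, the margin is 1.20 instead of 1.19, and only the 15% case drops below 80%. The power table already shows a larger sensitivity: for the same 15% reduction, moving the CON rate from 60% to 55% takes power from 81% to 73%. A slow start would cost more, but only with an average of 2.67-3.17 years, well short of what the plan says it will provide.

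The missing accrual pattern is a documentation gap that the trial statisticians can fill when they project events. Making the trial event-driven to protect a few points would be a trade-off, not a correction. These conclusions rest on exponential survival, 1% annual loss, the 60% CON rate and the assumed accrual shapes.
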